#### B. Study Type and Design

Menthol smokers (n=800), stratified by race and gender, who are not interested in quitting nicotine will be randomized 1:1 into a 12-week open label, non-inferiority trial comparing a 4th generation nicotine salt-based pod-system EC in menthol or tobacco flavoring. Each group will be provided a 12-week supply of EC 5% nicotine concentration in either menthol or Virginia tobacco and will complete 4 check-in sessions to facilitate switching to EC. The primary outcome is the proportion who make a complete or predominant switch to EC at week 12, where complete switching is defined as exclusive use of EC, biochemically confirmed with CO < 6, and predominant switching is defined as use of EC with > 50% reduction in CPD. Secondary outcomes include acceptability and long-term effectiveness. Follow-up will continue through week 26 to examine long-term maintenance of EC product use and smoking behavior under naturalistic conditions. Participants will be recruited and enrolled in collaboration with The University of Kansas Health System and Swope Health Central (Swope), a federally qualified health center serving a predominately AA population, that has been the site for our previous trials.

**Why a non-inferiority trial?** Non-inferiority trials are executed when one product is anticipated to be 'not unacceptably worse than' a comparator product and have value when it is feasible to sacrifice some degree of benefit to gain advantages provided by another product.  In the case of EC flavoring, the tradeoff of lower efficacy and acceptability of tobacco EC to adult menthol smokers may be well worth the advantages gained in youth and young adult initiation so long as the difference between tobacco and

menthol EC is not so large that adult menthol smokers are unwilling to use tobacco EC. The alternative would be a superiority study, but these are used to conclude that one product is better than the other, and at the time of this proposal there is no data supporting this approach that menthol EC are more effective than tobacco EC at facilitating a switch from tobacco cigarettes to EC or vice versa. Rather, data from our RCT and other studies suggest that tobacco EC are non-inferior to menthol EC in terms of effectiveness and acceptability to adult users, but a fully powered RCT is needed.

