#### C. Sample size, statistical methods, and power calculation

Sample size calculation. The aim of this non-inferiority trial is to establish that tobacco EC are not inferior to menthol EC in terms of the primary outcome, which is the proportion of menthol smokers who make a complete or predominant switch to EC, defined as use of EC along with a > 50% reduction in cigarettes from baseline to week 12. We assume 1) based on our RCT, that 73% in the menthol EC group will be complete or predominant switchers at week 12. We arrived at the 73% estimate at week 12 by examining the trend in switching from week 2 to week 6 in our RCT. Specifically, we noted a 12% reduction in switching from week 2 to week 6 and assumed that a similar trend would continue through week 12. Given an 85% switch rate in the menthol EC group at week 6 in our RCT and assuming a 12% reduction in switching from week 6 to 12, gives us a 73% switch rate at week 12. We also assume 2) to prove non-inferiority, the proportion in the tobacco EC group that are complete and partial switchers at week 12 will be similar to the menthol EC as long as it is greater than 64%. So, we can assume that P1=the proportion in the tobacco EC group that will be complete or predominant switchers at week 12=0.64 and that P2= the proportion in the menthol EC group that will be complete or predominant switchers at week 12=0.73. Then to test for noninferiority we have the following hypotheses: H0 (null hypothesis): P1-P2  $\leq$  -0.09 and H1 (alternative hypothesis): P1-P2 > -0.09. Following these assumptions 400 per group gives us 82% power with a Type 1 error rate of 2.5% using a normal approximation test for non-inferiority. Sample size calculations were done with PASS 16.0.4. **Basis for sample size calculations.** Estimates for non-inferiority trials are guided by an effectiveness ratio that indicates how effective one product is relative to another product and is determined from estimates on the outcome of interest and the a priori difference threshold. The FDA and other regulatory bodies have established an effectiveness ratio of  $\geq$  80% to indicate bioequivalence (i.e., non-inferiority). This is the criterion that we used in determining sample size for this study. Recent tobacco non-inferiority studies, including a tobacco harm reduction study comparing EC to heat-not-burn, have used a difference threshold of 15%.  Using this 15% threshold and our estimate of a 73% complete or predominant switch rate in the menthol EC group gives us an effectiveness ratio of 79% (.58/.73), which is under the criteria set by FDA. Raising the difference threshold to 14% would give us an effectiveness ratio of 81% (.59/.73). While this meets FDA criteria for non-inferiority, we felt that a difference of 14% was too large. Rather, we have gone with a more stringent difference threshold of 9%; at this threshold the proposed effectiveness ratio for our study is 88% (.64/.73), meaning that tobacco EC will be assumed to not be inferior to menthol EC if they are at least 88% as effective at facilitating a complete or predominant switch as menthol EC. This criterion places us well above the equivalence threshold set by the FDA and is more conservative than similar tobacco harm reduction non-inferiority studies, which we believe is a strength of this study. Missing **data.** We expect minimal (<5%) lost to follow-up at week 12 based on our recent studies, however those lost will be considered as non-complete or predominant switcher and will be imputed as such.

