
#### Statistical evaluation of study aims

#### Aim 1. Compare the effectiveness of menthol versus tobacco EC at facilitating switching at week

**12. Primary hypothesis.** *Participants randomized to tobacco EC (versus menthol EC) will demonstrate non-inferior rates of complete and predominant switching to EC (primary outcome). Complete switching is defined as exclusive use of EC, biochemically confirmed with CO < 6 ppm, and predominant switching is defined as use of EC with > 50% reduction in CPD.* We will test this hypothesis by calculating the 95% confidence interval for the difference in P1-P2, as defined above. To show noninferiority the upper limit of the confidence interval must be greater than or equal to 0.00 and lower limit of the confidence interval must be larger than -0.09. If the upper limit of the confidence interval is less than 0.00 then we cannot conclude noninferiority. If the upper limit is greater than or equal to 0.00 and the lower limit is less than or equal to -0.09 then the results would be inconclusive.

Rates of complete and predominant switching will also be compared separately by group using the chisquare test. Note, that we have not specified an a priori difference threshold for these analyses and, therefore, they are not testing noninferiority and should be considered exploratory. What these analyses will provide is an estimate of the proportion of complete switchers in the tobacco EC versus menthol EC group and, separately, an estimate of the proportion of predominant switchers in the tobacco EC versus menthol EC group.

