#### **B. Outcome**

#### EFFECTIVENESS (Aims 1 & 4).

Switching (Primary Outcome). The primary outcome is the proportion of menthol smokers who make a complete or predominant switch to EC, defined as use of EC along with a > 50% reduction in cigarettes from baseline to week 12. The 7-day Timeline Follow Back Interview (TLFB) will be used to assess participants cigarette and EC use patterns each day for the past 7 days at each visit (weeks 0, 4, 8, 12, 18, 26). The primary endpoint is, however, fixed at week 12. The TLFB is a reliable and valid way of collecting information about substance use quantity and frequency and, in tobacco research, has been corroborated against interactive voice response, butt counts (storing and returning the butts of cigarettes smoked), and biological measures for cigarettes smoked and puff topography for EC, supporting the strong validity of this self-report measure compared to other 'gold standard' measures. For each of the last 7 days participants will be asked to recall the number of cigarettes smoked and EC sessions vaped; following standard practice, an EC session is defined as at least 15 puffs or lasting around 10 minutes. For each EC session, participants will be asked to specify the device used (i.e., study provided versus something else) and the flavor (i.e., menthol, Virginia tobacco, something else).\* For non-study provided EC, detailed information will be collected about the type of EC (e.g., brand, podbased, disposable, refillable), flavor, nicotine concentration and, if available, whether the product is nicotine salt-based. To aid in recall and corroborate self-report, participants will be given dated bags to collect all EC. Bags will be returned at each visit during the intervention phase and used to confirm use of study provided EC (i.e., grams of e-liquid consumed) and protocol adherence (i.e., the number of pods vaped in the study provided versus non-study provided flavor). *Complete switching* is defined as any use of EC and no use of cigarettes in the past 7 days (i.e., 100% reduction in CPD from baseline), biochemically confirmed with an expired breath CO < 6 parts per million (ppm). CO is used for verification because cigarettes produce carbon monoxide as a byproduct of combustion, while heating an e-liquid does not generate CO. The < 6 ppm CO cutoff is more conservative than the  $\leq$  10 ppm cutoff that is commonly used and reflects the current state of knowledge for detecting recent cigarette smoking. Predominant switching is defined as those who report any use of EC along with a > 50%reduction from baseline in CPD. A > 50% reduction has been selected because it is a measure of acceptability of the EC products and is associated with substantial reductions in biomarkers of harm and exposure relative to continued smoking and is a common endpoint used in tobacco harm reduction studies. Partial switching will be defined as those who report any use of EC along with a  $\leq$  50% reduction from baseline in CPD. No switching (i.e., exclusive cigarette user) will be defined as those who reported no use of ECs and any use of cigarettes in the past 7 days. A potential fourth group, no use of e-cigarettes or combustible cigarettes, may occur. For all switching trajectories, use of EC will be corroborated with pod counts and objectively measured EC pod weights during the intervention phase.

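### Should the primary non-inferiority test be repeated with zero-cigarette reports that fail the carbon monoxide cutoff counted as failures?

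*Combined protocol and SAP*

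**What the plan says.** Section V.B (Outcome, Switching) and the sample size paragraph in section II.C define the primary composite in the same way. Section V.B describes it as a "complete or predominant switch to EC, defined as use of EC along with a > 50% reduction in cigarettes from baseline to week 12", and section II.C has it "defined as use of EC along with a > 50% reduction in cigarettes from baseline to week 12". Cigarettes and EC sessions come from a 7-day Timeline Follow Back interview (TLFB).

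Section V.B then defines the components:

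- Complete switching is any EC use with no cigarettes in the past 7 days, and it alone must be "biochemically confirmed with an expired breath CO < 6 parts per million (ppm"). The plan says this cutoff "reflects the current state of knowledge for detecting recent cigarette smoking", and in the same sentence calls it more conservative than the commonly used limit of 10 ppm or below.
- "Predominant switching is defined as those who report any use of EC along with a" reduction of more than 50% from baseline. No CO condition and no upper bound on the reduction is given.

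The aims in section I.A, the design summary in II.B and the Aim 1 analysis in II.C also attach CO to complete switching only. The Aim 1 rule is that the "lower limit of the confidence interval must be larger than -0.09" and the upper limit must be at least 0. If the upper limit is at least 0 but the lower limit is -0.09 or below, the result is inconclusive.

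**The concern.** The design is a "12-week open label, non-inferiority trial", so participants know their flavor when they report cigarettes. CO is measured in all participants at week 12 and is described as the biochemical check on smoking, yet it can never move anyone out of the primary composite. Pod counts and pod weights corroborate EC use, not cigarette use.

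If false zero-cigarette reports were more common in the tobacco-flavor arm, a real deficit could be hidden and non-inferiority claimed wrongly. The trial is meant to inform regulation of menthol EC, so a reader may expect a supportive repeat of the -0.09 test with contradicted reports scored as failures. None is planned. The separate comparisons of complete and predominant switching are exploratory and carry no margin. The Aim 2 comparison of mean CO change does not identify individual reports. The second version of the week-26 result deals with loss to follow-up.

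**Working it through.** **Inputs.** From section II.C: 400 per arm, margin 0.09, menthol rate 0.73 (292/400), type I error 2.5%, normal approximation. The documents give no share of zero-cigarette reporters with CO of 6 ppm or more and no arm imbalance, so every such share below is an assumption.

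**Classification.** Apply the section V.B definitions to an EC user who reports zero cigarettes (100% reduction):

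| Week-12 CO | Complete | Predominant (100% > 50%) | Composite |
|---|---|---|---|
| 3 or 5 ppm | yes | yes | success |
| 6 or 12 ppm | no | yes | success |

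The composite is the same at every CO value. The definitions settle the case without ambiguity.

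**The plan's own power.** With true rates of 0.73 in both arms, SE = sqrt(2 × 0.73 × 0.27 / 400) = 0.0314. Power = Φ(0.09/0.0314 − 1.96) = Φ(2.867 − 1.96) = 0.818, which matches the stated 82%.

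**Confidence limits after rescoring.** Limits = p1 − p2 ± 1.96 × sqrt(p1(1−p1)/400 + p2(1−p2)/400), where p1 is tobacco and p2 is menthol.

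Equal starting rates, equal rescoring:

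| Rescored per arm | Successes | Lower limit | Power at that common rate |
|---|---|---|---|
| none | 292 v 292 | -0.0615 | 82% |
| 2% | 284 v 284 | -0.0629 | 80% |
| 5% | 272 v 272 | -0.0647 | 78% |
| 10% | 252 v 252 | -0.0669 | 75% |

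Smallest tobacco-arm excess that makes the result inconclusive:

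| Menthol arm rescored | Last pass | First failure | Excess |
|---|---|---|---|
| none | 281 v 292, -0.08995 | 280 v 292, -0.0925 (upper +0.033) | 12 |
| 2% | 274 v 284, -0.0886 | 273 v 284, -0.0912 (upper +0.036) | 11 |
| 5% | 263 v 272, -0.0877 | 262 v 272, -0.0903 (upper +0.040) | 10 |
| 10% | 243 v 252, -0.0898 | 242 v 252, -0.0923 (upper +0.042) | 10 |

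If the tobacco arm starts 1 or 2 points lower (288 or 284 v 292; limits -0.0719 and -0.0822, both passing), an excess of 8 or 4 reaches 280 v 292.

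**Can the repeat change with no imbalance at all?** Yes.

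- 281 v 292 gives -0.08995 (pass). Rescore 8 in each arm (2%): 273 v 284 gives -0.0912 (inconclusive).
- 282 v 292 gives -0.0874 (pass). Rescore 20 in each arm (5%): 262 v 272 gives -0.0903 (inconclusive).

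In both pairs the observed difference is unchanged (-0.0275 and -0.025). Only the interval widens, because the rates move closer to 0.5. A changed result would therefore not by itself point to differential misreporting.

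**The case for a change.** The best case for adding the analysis is that it is cheap and bears on the headline claim. The CO data already exist, the primary analysis would be untouched, scoring contradicted reports as failures mirrors the plan's rule for participants lost at week 12, and fixing the rule in advance avoids choosing a cutoff after seeing results. The stakes can also be put in terms of false claims. If the true verified rates were 0.64 v 0.73, and self-report hid 2 or 3 points of that deficit in the tobacco arm, the chance of clearing -0.09 would rise from 2.5% to 8.9% or 15.1%. The plan's statement that the TLFB has been checked against other measures, "supporting the strong validity of this self-report measure", does not show that any misreporting is balanced between flavors.

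These facts and figures stand. The inference to a defect does not:

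- A reading of 6 ppm or more speaks against a report of zero cigarettes but leaves open a cut of more than half. The repeat would fail a zero-cigarette reporter at 6 ppm while passing someone who admits a few cigarettes at a higher CO. Reported reductions between 50% and 100% would stay unchecked.
- Readings from 6 to 10 ppm would pass the common cutoff that the plan itself names, so calling all of them contradictions is too strong.
- The documents suggest no mechanism for a flavor difference in false zero reports. Both arms get the same brand, nicotine strength and check-ins, payment does not depend on flavor returned, and people interested in quitting smoking are excluded.
- The planned comparisons of CO-verified complete switching and of mean CO change by arm could already reveal a marked imbalance.

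**Conclusion.** No change is needed. The absence of CO from the composite is consistent wherever the endpoint is defined, and following the plan as written answers the question it poses: the arm difference in EC use with a reported reduction of more than 50%. Reliance on self-report for the size of that reduction is a fair trade-off, since a single CO cutoff cannot verify a halving of consumption.

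The suggested repeat tests a stricter endpoint, so it cannot establish whether the primary conclusion survives. From equal arms at 73%, it would take an excess of 10 to 12 rescored tobacco-arm participants out of 400 to change the reading, and fewer if the arm starts lower. Near the margin, equal rescoring of 2% to 5% can do the same. These figures assume 400 analyzed per arm and the rescoring shares shown. They measure sensitivity and are not evidence that misreporting exists.

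The sponsor could usefully report, by arm, how many zero-cigarette reporters have a week-12 CO of 6 ppm or more and how many exceed 10 ppm, with the rescored interval as a descriptive companion. That is optional, and the primary analysis is sound without it.

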#### Biomarkers of interest include:

cotinine

- total NNAL (for nicotine-derived nitrosamine ketone NNK);
- 2-hydroxyethylmercapturic acid (HEMA) (for ethylene oxide);
- 2-hydroxy-3-butenyl-mercapturic acid and isomers (MHBMA) (for 1,3-butadiene);
- 3-hydroxy-1-methyl propyl-mercapturic acid (HMPMA) (for crotonaldehyde);
- 3-hydroxypropylmercapturic acid (3-HPMA) (for acrolein);

- S-phenylmercapturic acid (S-PMA) (for benzene);
- 2-cyanoethylmercapturic acid (CEMA) (for acrylonitrile);
- 2-hydroxypropylmercapturic acid (2-HPMA) (for propylene oxide)
- pyrene (1-OHP)
- matrix metalloproteinaise-8 (MMP8) and interleukin-9 (IL9) for airway epithelial cell inflammation
- 8-Epi-prostaglandin F2a (oxidative stress)
- 11-Dehydrothromboxane B2 (platelet activation)
- soluble intercellular adhesion molecule-1 (sICAM)

**ACCEPTABILITY (Aim 3).** Detailed assessment of EC product use, effects on withdrawal, craving, and dependence, and subjective and sensorial effects will be evaluated at all study visits to compare acceptability by group (menthol versus tobacco EC).

**Grams of study e-liquid consumed (weeks 4, 8, 12).** Use of the study EC in the flavor provided will be objectively measured by asking participants to bring all used, unused, or partially used pods to the weeks 4, 8, and 12 study visits. Pods will be weighed prior to their distribution and then upon return to derive *total grams of study e-liquid in the flavor provided consumed* from weeks 0-12. In our RCT, 95%, 92%, and 98% of participants returned their pods at weeks 2, 4, and 6, respectively, and there was no evidence of cheating – i.e., returned pods were in the flavor provided by the study – suggesting that participants used only the study provided pods throughout the intervention phase. For unreturned pods, we will conservatively assume 0 grams of e-liquid consumed. Objective measurement of pod weights was strongly correlated with number of e-cigarette sessions per day measured by TLFB in our RCT (r=0.58, p < .001).

**Flavor usage (all visits).** Based on our RCT, we expect low rates of non-study EC product use, but we will conduct rigorous assessments of adherence to EC flavoring during the intervention phase and continued use during the long-term follow-up phase. From the TLFB, we will summarize the proportion of total EC that were in the study provided versus a non-study provided flavor. From pod counts, we will summarize the number of pods returned by flavor (i.e., menthol, Virginia tobacco, other) and derive an estimate of the proportion of total pods returned that were in the study provided flavor.

**Craving (all visits).** Craving for cigarettes will be assessed using the *Questionnaire on Smoking Urges-Brief* **(QSU)** and its companion, the *Questionnaire on Vaping Craving-Brief* (*QVC*) will be assessed at each visit and compared between groups. Both measures yield a total score and two factor scores: desire to smoke/vape and intention to smoke/vape. The QVC yields a third factor, positive outcome of vaping.

**Withdrawal (all visits)**. The *Minnesota Tobacco Withdrawal Scale*will be used to rate eight withdrawal symptoms in the past 24 hours: anger, anxiety, concentration, craving, hunger, sadness, and sleep. Items are rated from 1 (strongly disagree) to 5 (strongly agree). Scores will be summarized overall and for each construct.

**Dependence (all visits)**. Following guidance from the TCORS dependence workgroup, we will include a compendium of dependence measures, validated for use in assessing both cigarette and EC related dependence, to cover all components of dependence (i.e., quantity and frequency of use, tolerance, perceived benefits, withdrawal symptoms, cravings/urges to use, use despite harm, impaired control, automaticity, preferred over competing rewards, and sensory dependence.) We have intentionally selected cigarette dependence measures that have parallel EC dependence measures to allow for direct comparison in dependence across products by group. These measures include:

• Patient Reported Outcomes Measurement Information System (PROMIS) Nicotine Dependence Item Bank  and its companion the *E-Cigarette Dependence Scale*.

• *Penn State Cigarette Dependence Index* (PS CDI) and its companion the *Penn State Electronic Cigarette Dependence Index* PS ECDI)

• Wisconsin Inventory of Smoking Dependence Motives (WISDM) and its companion the *E-Cigarette* Wisconsin Inventory of Smoking Dependence Motives (eWISDM). Dependence will be summarized for the WISDM total score as well as the average score on the Primary Dependence Motives (i.e., Automaticity, Loss of Control, Craving, and Tolerance.

• *Time to First Cigarette* and *Time to First EC of the Day*. This single item from the Fagerstrom Cigarette Dependence Scale is the best indicator of dependence in a sample of mostly light smokers ( $\leq$  10 CPD).

**Subjective effects of vaping (all visits).** The 12-item *Modified Cigarette Evaluation Scale* adapted for e-cigarettes will be administered at all time points to access product satisfaction and subjective and sensorial effects of vaping by group (menthol versus tobacco EC). Questions are answered on 7-point scale from 1 (not at all) to 7 (extremely) and assess *vaping satisfaction* (was vaping

satisfying, did the e-cigarette taste good, did you enjoy vaping), *enjoyment of respiratory tract sensations* (did you enjoy the sensations in your throat and chest), *psychological reward* (did vaping calm you down, did vaping make you feel more awake, did vaping make you feel less irritable, did vaping help you concentrate), *craving reduction* (did vaping immediately relieve your craving for a cigarette), and *aversion* (did vaping make you dizzy, did vaping make you nauseous). The single item, "Did the e-cigarette taste good?" will be used as a proxy for flavor liking as has been done in previous studies. The 23-item *Sensory E-cigarette Expectancies Scale*, particularly the subscales related to taste/smell ('I like the taste of vaping', 'I like the smell of vaping,' 'I like the flavor of vaping') and pleasure/satisfaction ('I like how vaping makes me feel good physically,' 'I like the feeling of satisfaction that I get from vaping') will be administered for secondary assessment of product satisfaction and acceptability.

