Participants randomized to tobacco EC (versus menthol EC) will consume comparable amounts of study provided e-liquid (measured in grams) and demonstrate comparable reductions in cigarette-related withdrawal, craving, and dependence. Subjective effects of vaping will also be compared between groups. Each of these measures are on a quantitative scale and, given the sample size, we can assume the central limit theorem will hold. Thus, we will calculate the mean e-liquid consumption over 12 weeks and its corresponding standard deviation by group. We will then compare the difference in these means between the groups using a two-sample t-test and calculate the corresponding 95% confidence interval. Given that we expect to show noninferiority in tobacco EC versus menthol EC, we expect to find no difference in e-liquid consumption and, therefore, the confidence interval for the difference between groups will contain 0.00. If noninferiority is not seen, then we may see a difference in the e-liquid consumption by group. For change in cigarette-related withdrawal, craving, dependence, and subjective effects of vaping, we will calculate the mean change and corresponding standard deviation for each of these measures by group. We will then conduct the two-sample t-test comparing the means between the groups while also reporting the corresponding 95% confidence intervals. Given that we expect to show noninferiority in tobacco EC versus menthol EC, we expect to find no difference in cigarette-related withdrawal, craving, dependence, or subjective effects of vaping. This means that we expect to fail to reject each of the t-tests and expect that each confidence interval for the difference between groups will contain 0.00. However, as described in Aim 2, if any of these variables are different when noninferiority is seen, we will then utilize logistic regression to identify any phenotypic or consumption patterns – e.g., gender, age, socioeconomic status, study-related side effects, adverse events, change in CPD, cigarette-related withdrawal, craving, dependence, EC usage and grams of e-liquid consumed, subjective effects of vaping, baseline smoking history, or psychosocial factors -- may explain this difference and the regression analyses undertaken will illuminate reasons for the difference.

If noninferiority is not seen, then we would expect to see a difference in one or more of these measures.

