#### **Procedures and Methods**

An overview of major study events is provided in the adjoining table.
---

	Screen*	Enroll						Primary Outcome		
		∘Wk 0	Wk 1*	Wk 2*	Wk 3*	Wk 4	Week 8	Wk 12	Wk 18	Week 26
Remuneration		\$40				\$60	\$60	\$60	\$40	\$40
EC Check-ins		Х	Х	Х	Х	Х	Х	Х		
Dispense EC		Х				Х	Х	Х		
Screening	Х	Х								
Consent		Х								
Assessments		Х				Х	Х	Х	Х	Х
Spirometer		Х						Х		Х
CO		Х				Х	Х	Х	Х	Х
Blood Pressure		Х						Х		Х
Exhaled Breath		х				Х	Х	×		
Condensates								Х		
Urine and Saliva		Х						Х		Х

\* Over the phone

**Initial Screening.** The initial screen will review inclusion/exclusion criteria. Those eligible will be scheduled to complete final eligibility screening within 21 days. All ineligible smokers will be referred to local resources when applicable.

**Final Screening and Enrollment (Wk 0).** Final eligibility screening will be conducted in person and will consist of a pregnancy test on women of childbearing age and obtaining informed consent.

**Electronic cigarettes (Wk 0, 4, 8, 12).** Participants will be provided a 12-week supply of VUSE 5% nicotine concentration in either menthol or Virginia tobacco that will be dispensed at the weeks 0, 4, and 8 in-person visits (4-week supply @ each visit). To aid in recall and assessment of fidelity to protocol, participants will be given dated bags to collect all EC. Bags will be returned at each visit during the intervention phase to confirm use of EC (i.e., grams of e-liquid consumed and count of pods) as well as protocol adherence.

EC Check-in Visits (Wks 0, 4, 8, and 12). Check-in sessions, each lasting approximately 20 minutes, will be completed in person at Wks 0, 4, 8, and 12 and by phone at Weeks 1, 2, and 3. The number of sessions is consistent with our previous studies where we have achieved visit completion rates of ~ 80%.

**Spirometer.** Lung function will be assessed via spirometry. We will carefully monitor respiratory symptoms over time using standardized measures. Spirometry will be completed at Wks 0, , 12, and 26.

**Carbon Monoxide.** Exhaled air carbon monoxide (CO) is an immediate, non-invasive method of biochemically verifying smoking status. At Wks 0, 4, 8, 12, 18, and 26, all participants will breathe into a Micro-3 Smokerlyzer (Bedfont Scientific) for the purpose of determining smoking levels.

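### Counting unreturned pods as 0 g is not conservative for the between-arm comparison of e-liquid use in Aim 3

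*Combined protocol and SAP*

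**What the plan says.** Section V.B (Acceptability, Aim 3) has participants bring every pod, used or not, to the week 4, 8 and 12 visits. "Pods will be weighed prior to their distribution and then upon return to derive" the total grams consumed in the assigned flavor over weeks 0-12. The rule for the rest is: "For unreturned pods, we will conservatively assume 0 grams of e-liquid consumed". No reason is given for calling this conservative.

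The hypothesis for Aim 3 (section II.C) is that the tobacco arm "will consume comparable amounts of study provided e-liquid (measured in grams"). For the analysis, "We will then compare the difference in these means between the groups using a two-sample t-test", with a 95% confidence interval. The expected result is stated in advance: "we expect to find no difference in e-liquid consumption and, therefore, the confidence interval for the difference between groups will contain 0.00".

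On how often pods come back, section V.B reports: "In our RCT, 95%, 92%, and 98% of participants returned their pods at weeks 2, 4, and 6, respectively". These figures are not split by arm. No sensitivity analysis and no by-arm report of pod return is planned for grams. Week-26 switching, by contrast, is to be reported in two ways: with those lost counted as not switched, and for completers only.

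**The concern.** A pod that does not come back may have been used and thrown away, left at home, or lost unused. Only the last is truly 0 g, so zero is the smallest value the pod could have.

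That protects against overstating use in a single arm. The Aim 3 question is a different one: do the arms use similar amounts? If both arms return equally, scaling both means down scales the difference down too, and a non-significant test becomes easier to obtain. That favors the trial's own hypothesis. If the arms return unequally, the gap in return is converted directly into a gap in grams, which can create a difference or hide one. The trial is open label and the arms differ in flavor, so unequal return is possible.

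Non-return could also be more common than in the earlier trial. Returns there were at weeks 2, 4 and 6; here they are four weeks apart. Participants who miss a dispensing visit are still delivered pods (section II.E, Treatment Overview), so pods can be used without being brought back on schedule. At stake is the reading of an objective measure of acceptability.

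**Working it through.** **The plan's own figure.** The documents give no power figure for grams. The only one is 82% for the week-12 primary test. It reproduces: with 0.73 in both arms, margin 0.09, one-sided 2.5% and 400 per arm, SE = sqrt(2 × 0.73 × 0.27 / 400) = 0.0314, and power = Φ(0.09/0.0314 − 1.96) = 81.8%. That test does not use grams.

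**Inputs from the documents.** 400 per arm; two-sample t-test with 95% interval; three dispensing periods (weeks 0, 4, 8); overall pod return of 92% to 98% in the earlier trial.

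**Assumptions, not in the documents.** Coefficient of variation (CV) of grams c = 0.7, with 0.5 to 1.0 as a range; equal use in the three periods; non-return unrelated to the amount used within an arm; every by-arm return rate below; normal approximation to the t-test.

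**Formulas.** Let μ be the true mean in an arm and r its return share. After zero-filling:
- Mean = rμ.
- Pattern A, non-return independent over the three periods: variance = μ²{[3r(1−r) + 9r²]/9 × (c² + 1) − r²}.
- Pattern B, the same people never return pods: variance = μ²{r(c² + 1) − r²}.
- The observed difference is r_T μ_T − r_M μ_M (T tobacco, M menthol), with SE = sqrt((V_T + V_M)/400).

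**1. Equal return, true 15% tobacco deficit (μ_M = 1, μ_T = 0.85), c = 0.7**

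| Return, both arms | Observed difference | Power, pattern A | Power, pattern B |
|---|---|---|---|
| 100% | −0.150 | 90% | 90% |
| 92% | −0.138 | 88% | 83% |
| 80% | −0.120 | 83% | 69% |

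Worked case, pattern A at 80%: V_M = 0.393, V_T = 0.284, SE = sqrt(0.677/400) = 0.0411, and 0.120/0.0411 = 2.92, giving 83%. Under pattern A the absolute variance in the menthol arm falls (0.490 at full return, 0.393 at 80%). Power drops because the difference shrinks faster than the SE. With no true difference, equal return leaves the false-positive rate at 5%.

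**2. Unequal return, no true difference, c = 0.7, pattern A**
- 90% (T) versus 95% (M): difference 0.90 − 0.95 = −0.05; SE = sqrt((0.442 + 0.466)/400) = 0.0476; false-positive rate 18% instead of 5%.
- 92% (T) versus 98% (M), the extremes of the earlier trial's overall range: difference −0.06; SE 0.0483; rate 24%.

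Over CV 0.5 to 1.0 and both patterns, these rates run 11-30% and 14-40%.

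**3. Unequal return hiding a true difference.** With a true 10% tobacco deficit and return of 95% (T) versus 85% (M), the observed ratio is 0.90 × 0.95/0.85 = 1.01. The deficit has gone, and the rejection rate is about 5%.

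**The case against.** The strongest reply is that non-return will be rare and balanced. The only pod-return evidence is 92-98%. Participants get dated bags and $20 at each of weeks 4, 8 and 12 for returned pods, whatever the flavor, and loss by week 12 is expected to be under 5%. A missed visit need not lose the pods: they can be brought to a later one, and the outcome is a 12-week total. Treating each missed period as permanently zero, as the calculation does, therefore overstates the effect of intermittent misses. All of this stands. At equal return of 92% or better, the loss of power is small under pattern A and moderate under pattern B.

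A reader might infer several stronger things that the documents do not support:
- *That return will be about 80%.* The statement that earlier studies "achieved visit completion rates of ~ 80" per cent concerns check-in sessions; it is not a pod-return rate.
- *That a 10- to 15-point gap between arms is likely.* No by-arm rate is given; such gaps are assumptions only.
- *That zero-filling always adds variance.* Under pattern A absolute variance falls; it rises under pattern B.
- *That 0 g is simply wrong, or that grams is the main acceptability outcome.* A lost unused pod is 0 g, and the plan lists grams first without ranking the Aim 3 measures.
- *That the rule reaches the primary outcome.* Section V.B says "use of EC will be corroborated with pod counts and objectively measured EC pod weights during the intervention phase", but switching is defined from the timeline follow-back and exhaled CO, and nothing applies the 0 g value there.

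What the reply does not answer is the word conservative. Low expected non-return makes the problem smaller; it does not make zero a cautious choice for a comparison, and the plan has no check that would reveal an imbalance.

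**Conclusion.** The concern holds for the between-arm comparison of grams. Zero is a lower bound that attenuates a true difference when return is equal and biases it in either direction when return differs.

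The size depends on unknowns. At CV 0.7, equal return of 92% costs 2 to 7 points of power for a true 15% deficit (90% to 88% or 83%). A 5- or 6-point gap in return with no true difference raises the false-positive rate to 18% or 24% under independent non-return. A 10-point gap can erase a true 10% deficit. The CV, the by-arm rates and the independence of non-return from use are all assumed, and late return of pods could make the effect smaller.

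This is a moderate issue in a secondary aim. The week-12 non-inferiority test and its 82% power are untouched. The plan should still change, because the remedy is cheap and the present rule leans toward the result the trial expects.

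**What to change.** In section V.B (grams of study e-liquid), delete the word conservatively and drop the 0 g rule as the main analysis. Instead:

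1. Treat grams for pods still unreturned at week 12 as missing, so that pods brought back late count at their measured weight.
2. Multiply impute those grams from the participant's returned-pod weights in other periods, pods dispensed, arm, race, gender, and timeline follow-back EC sessions where available.
3. Report two bounding sensitivity analyses: 0 g and full-pod use for every unreturned pod.
4. Report pod return rates by arm at weeks 4, 8 and 12.

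The cost is a few lines of text and some extra programming; no new data collection is needed. The imputation assumes data missing at random, which the two bounds check. The session data have limits: they cover only the 7 days before a visit, may be absent when the visit was missed, and correlated 0.58 with pod weight in the earlier trial (about 34% of variance, 0.58² = 0.34). They should support the imputation model, not carry it alone.
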